2.3.2 Benefit Assessment

There is no guarantee that participants will benefit from taking part in this research study. Participant's symptoms of PTSD may improve while taking part in this study. Information obtained from this study may help doctors and researchers to improve treatment and treatment access for PTSD and other mental health conditions in the future.

3.0 Objectives and Endpoints

The overall objective of this study is to use standard clinical measures to explore the safety and feasibility of open-label MDMA-assisted therapy with a divided-dose of MDMA in the group therapy context in reducing PTSD symptomology in veterans.

4.0 Study Design

4.1 Overall Design

This Phase 2, open-label, non-randomized, 3-cohort study assesses the feasibility and safety of MDMA-assisted group therapy for the treatment of PTSD in veterans. The study will be conducted in up to N=18 participants, recruited in three cohorts of up to six participants and receive therapy sessions throughout their participation in these groups.

For each participant, the study will consist of:

- **Screening Period and Enrollment:** phone screen, informed consent, eligibility assessment, and enrollment of eligible participants.
- **Preparatory Period:** Preparatory Sessions, and baseline assessments.
- **Treatment Period:** two Experimental Sessions, and four Integrative Sessions following each Experimental Sessions.
- **Follow-up Period and Study Termination:** Primary Outcome assessment and Study Termination visit.

After the Screening Period and Enrollment, eligible participants will begin a ~4-week Preparatory Period. Participants will attend four, 90-minute, non-drug, Preparatory Sessions, including three group sessions and one individual session. Following the Preparatory Period, participants will begin an ~8-week Treatment Period comprised of two Experimental Sessions, each followed by four Integrative Sessions.

MDMA will be administered twice during the Treatment Period: one Individual Session and one Group Session. The Experimental Sessions will last ~8 hours. Four 90-minute Integration Sessions, each one week apart, will follow the Individual Experimental Session. The first Integration Session will be Individual, occurring the morning following Experimental Session 1, and the other three will be Group Integration Sessions. Finally, four Group Integration Sessions, each a week apart, will follow the Group Experimental Session. Integrative Session 2.1 will take place the morning after Experimental Session 2. A study termination visit will be conducted at the end of the study.

4.2 Scientific Rationale for Study Design

PTSD is a chronic and disabling stress-related condition associated with serious adverse health outcomes and identifying novel treatments with durable effectiveness is timely and important. Military veterans are disproportionately affected by PTSD in comparison to the general population and group therapy is widely used in VA clinics to treat PTSD. This open-label study will evaluate the feasibility and safety of MDMA-assisted group therapy for the treatment of PTSD in veterans. The first Experimental session will be administered in an individual treatment session with two co-facilitators in order to familiarize each participant with the therapeutic experience. The second Experimental session will be administered in a group treatment session in which all cohort participants will simultaneously receive MDMA in the presence of four trained co-facilitators. The CAPS-5 is considered the international gold standard for the diagnosis of PTSD and the assessment of PTSD symptom severity. Safety data will be collected throughout. The data collected in this study will be analyzed both individually and by cohort.

Experimental Sessions, both Individual and Group, will primarily follow the treatment approach outlined in the Treatment Manual for individual participants. Previously reported studies using group sessions in MDMA studies will also inform the format of Group Experimental Sessions in this protocol. As part of the protocol development process, the team of MAPS-trained therapists will adapt the Treatment Manual in order to apply to a group therapy context.

4.3 Justification for Dose

Similar MDMA doses to those proposed in this study have been safely used in previous Phase 2 studies sponsored by MAPS. Phase 2 studies indicate that 63, 84, and 105 mg MDMA (equivalent to 75, 100, and 125 mg MDMA HCl) initial doses followed by a supplemental dose are active and effective at reducing PTSD symptomology following two to three Experimental Sessions. MDMA initial doses with an optimal risk-benefit ratio range from 63 mg dose (Cohen's d Independent Groups Pre-test Post-test [dIGPP]=2.73, N=7) to 125 mg dose (Cohen's d IGPP=0.77, N=58) of MDMA with a 2-session treatment package. In Phase 2 studies, the sponsor observed a 36.4 point mean decrease in CAPS-4 scores among active dose (63 to 105 mg MDMA, equivalent to 75 to 125 mg MDMA HCl) participants receiving two Experimental Sessions (N=72). Larger doses have been safely administered in MP2 (126 mg and 63 mg supplemental MDMA, equivalent to 150 mg and 75 mg MDMA HCl) and in Phase 1 studies (126 to 135 mg MDMA, equivalent to 150 mg and 160 mg MDMA HCl). The results of these Phase 2 studies led to the selection of 120 mg MDMA as the initial active doses.

This open-label study will examine the effects of a divided-dose of 134 mg to 150 mg of MDMA (equivalent to 160 mg to 180 mg MDMA HCl) administered in two Experimental Sessions. Participants will receive an initial dose of 100 mg and a supplemental dose of 34 mg or 50 mg MDMA (equivalent to 120 mg and a supplemental dose of 40 mg or 60 mg MDMA HCl) at 1.5-2 hours after initial ingestion, unless tolerability issues emerge with the initial dose or the participant declines, see [Section 6.5 Dose Modification](#). Strength of supplemental dose will be the same for all participants and will be determined by drug supply availability at the start of the trial. The initial active dose is expected to produce all commonly reported effects of MDMA. The supplemental dose prolongs the subjective effects of MDMA without producing physiological effects much greater than peak effects occurring after the initial dose and will be administered unless there is a reason to withhold. Total amounts of MDMA to be administered per Experimental Session range from 100 mg to 150 mg (equivalent to 120 mg to 180 mg MDMA HCl).

Table 2: Dose Regimen of MDMA

Experimental Session	Initial Dose	Supplemental Dose*	Min-Max Cumulative Dose
1 (Individual)	100 mg	34 or 50 mg	100 to 150 mg
2 (Group)	100 mg	34 or 50 mg	100 to 150 mg
Total Cumulative Dose			200 to 300 mg

*Unless tolerability issues emerge with the initial dose or the participant declines.

Examples of tolerability issues may include: if a participant experiences a severe adverse event after administration of MDMA during an experimental session, or they experience clinical signs and symptoms that may suggest end organ effects as specified in the protocol, the supplemental dose may not be administered. Examples of these symptoms include chest pain, shortness of breath, neurological deficit or confusion, or other potential indicators of end organ effects that will prompt additional vital sign measurements, and intervention if appropriate. Please refer to [Table 4: Risk Assessments](#) for additional details.

4.4 End of Study Definition

The end of the study is defined as the date of the last visit of the last participant in the study. A participant is considered to have completed the study if they have completed all periods of the study including the last visit.

The sponsor has the right to discontinue this study at any time. If the trial is prematurely terminated, the investigator is to promptly inform participants and will ensure they receive appropriate therapy, follow-up, and plan moving forward. If the study is prematurely discontinued, all procedures and requirements pertaining to retention and storage of documents will be observed. All other study materials will be returned to the sponsor and will be treated in accordance with country regulations.

5.0 Study Population

Prospective approval of protocol deviations to recruitment and enrollment criteria, also known as protocol waivers or exemptions, is not permitted.

5.1 Inclusion Criteria

Participants are eligible to be included in the study only if all the following criteria apply:

Age

1. Be 18 years of age at the time of signing the informed consent.

Type of Participant and Disease Characteristics

2. Are a military veteran.
3. At Screening, meet DSM-5 criteria for current PTSD
4. Fluent in speaking and reading the predominantly used or recognized language of the study site.
5. Able to swallow pills.
6. Agree to have study visits video-recorded, including Experimental Sessions, IR assessments, and non-drug therapy sessions.
7. Able to identify appropriate support person(s) to stay with the participant on the evening of the Experimental Session, see [Section 8.2.4 Support Person](#).
8. Able to provide a contact (relative, spouse, close friend, or other support person) who is willing and able to be reached by the investigators in the event of the participant becoming unwell or unreachable.
9. Agree to inform the investigators within 48 hours of any medical conditions and procedures.

Weight

10. Body weight of at least 48 kilograms (kg).

Sex and Contraceptive/Barrier Requirements

11. For participants assigned female sex at birth:
 - A participant is eligible to participate if not pregnant or breastfeeding, and one of the following conditions applies:
 - Is not able to become pregnant as defined in [Appendix 2: Contraceptive and Barrier Guidance](#).
 - OR
 - Is a person able to become pregnant (PABP) and using a contraceptive method that is highly effective, with a failure rate of <1%, as described in [Appendix 2: Contraceptive and Barrier Guidance](#), during the study intervention period and for at least 10 days after the last dose of study intervention. The investigator should evaluate the potential for contraceptive method failure (e.g., noncompliance, recently initiated) in relationship to the first dose of study intervention.
 - A PABP must have a negative highly sensitive pregnancy test (urine or serum as required by local regulations) at study entry and prior to each experimental session.
 - The investigator is responsible for review of medical history, menstrual history, and recent sexual activity to decrease the risk for inclusion of a participant with an early undetected pregnancy.

Informed Consent

12. Capable of giving signed informed consent as described in [Appendix 1: Regulatory, Ethical, and Study Oversight Considerations](#), which includes compliance with the requirements and restrictions listed in the ICF and in this protocol.

5.2 Exclusion Criteria

Participants are excluded from the study if any of the following criteria apply:

Medical Conditions

1. Have evidence or history of significant medical disorder

2. Have symptomatic liver disease
3. Have a marked baseline prolongation of QT/QTc interval (e.g., repeated demonstration of a QTc interval >450 milliseconds [ms] corrected by Bazett's formula)
4. Have a diagnosis of uncontrolled hypertension

Prior/Concurrent Clinical Study Experience

5. Current enrollment in any other clinical study involving an investigational study treatment or any other type of medical research, unless approved by the Medical Monitor.

Other Exclusions

6. Sensitivity to any of the study interventions, or components thereof, or drug or other allergy that, in the opinion of the investigator or Medical Monitor, contraindicates participation in the study.
7. Previous participation in a MAPS-sponsored MDMA clinical trial.
8. Have any current problem which, in the opinion of the investigator or Medical Monitor, might interfere with study participation.

5.3 Lifestyle Considerations

All participants must agree to the following lifestyle modifications at time of signing the ICF and throughout the study.

Participants are eligible to enroll in the study if they:

- Are willing to complete all activities described in the ICF, which include MDMA dosing, therapy sessions, follow-up sessions, completing evaluation instruments, and all necessary telephone contact.
- Are willing to engage in group therapy sessions where there is a risk of a loss of confidentiality.
- Agree to not participate in any other interventional clinical trials during the duration of this study, without prior approval of the Medical Monitor.
- Agree not to take any new or prohibited medications or recreational drug substances during the course of the study without first discussing with the investigator in consultation with the Medical Monitor.
- Agree to not begin a new form of mental healthcare during the screening or treatment phases of the trial, without first discussing with the PI in consultation with the Medical Monitor.
 - It is acceptable for participants to continue ongoing mental healthcare, if it is not increased in frequency or specifically excluded by the study protocol.
 - All ongoing therapies should be documented by the site and discussed with the Medical Monitor prior to enrolment to avoid confounding treatment effects. In some instances, the Medical Monitor may request that the participant delay enrolment until their planned course of therapy is complete and an integration period has elapsed.

5.3.1 Leading up to the Experimental Session

- Agree to take nothing by mouth except alcohol-free liquids after 12:00 A.M. (midnight) the evening before each Experimental Session.
- Agree not to use caffeine or nicotine for 2 hours before each Experimental Session.

- Refrain from the use of any psychoactive medication not approved by the research team from Baseline through Study Termination.
- Are willing to comply with medication requirements per protocol (refer to [Section 6.8 Concomitant Therapy](#)). Medications will only be discontinued after enrollment per clinical judgment of the site physician in consultation with the prescribing physician.
- Are able to decrease dose of allowable opiates (per Sections [6.8.2 Permitted Concomitant Medications](#) and [6.8.3 Prohibited Medications](#)), if used for pain management, leading up to the Experimental Session in order to avoid taking the medication for at least 12 hours prior to the initial IMP administration and 24 hours after. During this period, the participant will be allowed to take the medication if needed for intolerable pain flare-ups.
- Agree that, for 5 half-lives plus 1 week preceding each Experimental Session to refrain from:
 - Taking any herbal supplement (except with prior approval of the research team).
 - Taking any nonprescription medications (except for non-steroidal anti-inflammatory medications or acetaminophen/paracetamol unless with prior approval of the research team).
 - Taking any prescription medications (with the exception of birth control pills, thyroid hormones, or other medications approved by the research team).

5.3.2 Post Experimental Session

- Are willing to be accompanied home after the Experimental Sessions either by the support person or escort, see [Section 8.2.4 Support Person](#).
- Are willing to refrain from operating a vehicle for 24 hours following initial medication administration.

5.3.3 Meals and Dietary Restrictions

- Agree to take nothing by mouth except alcohol-free liquids after 12:00 A.M. (midnight) the evening before each Experimental Session.

5.3.4 Caffeine, Alcohol, and Tobacco

- Participants must agree not to use caffeine or nicotine (including nicotine patches) for 2 hours before and at least 6 hours after the initial dose during each Experimental Session.
- Prior to each dosing session, participants will abstain from alcohol for 24 hours before the planned start of dosing until after they leave the clinical site the following day.

5.4 Screen Failures

A screen failure occurs when a participant who consents to participate in the clinical study is not subsequently entered in the study. A minimal set of screen failure information is required to ensure transparent reporting of screen failure participants to meet the Consolidated Standards of Reporting Trials (CONSORT) publishing requirements and to respond to queries from regulatory authorities. Minimal information includes demography, screen failure details, eligibility criteria, and any serious adverse event (SAE). Any participant who fails screening should be offered a referral to an outside therapist.

Individuals who do not meet the criteria for participation in this study (screen failure) may be rescreened if approved by the investigator in consultation with the Medical Monitor. Rescreened

participants should be assigned a new screening number for every screening/rescreening event and should sign a new copy of the ICF.

5.4.1 Pre-Dosing Early Termination

‘Pre-Dosing Early Terminations’ are defined as participants who were deemed eligible and enrolled in the study at Enrollment Review but are deemed ineligible prior to the first Experimental Session, first IMP administration. These participants may fail to meet all Inclusion Criteria and may meet one or more Exclusion Criteria or withdraw consent prior to the first Experimental Session, IMP administration. All enrolled participants, even Pre-Dosing Early Terminations, will be maintained in the Electronic Data System (EDC). Pre-Dosing Early Terminations are not considered evaluable.

Pre-Dosing Early Terminations may be identified through review of medical history, assessments, measures, laboratory results, or conversations with the participant. At any time prior to first IMP administration, if a potential participant is deemed to be ineligible, classify as a Pre-Dosing Early Termination, notify the potential participant that they are not eligible for the study, and do not schedule additional assessments. Do not perform the next visit. Pre-Dosing Early Terminations will be provided a plan moving forward as described in [Section 8.4.4 Plan Moving Forward](#).

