6.8.1 Psychiatric Medications

Psychiatric medications approved for treatment of PTSD, are under investigation for treatment of PTSD, or which are used off-label to treat symptoms of PTSD are not permitted during the trial and must be tapered during the Preparatory Period. If the participant is being treated with any such medication(s) at enrollment, the participant will be encouraged to discuss medication tapering with their outside treating physician and will be required to give the site physician permission to do so as well. The medications will then be tapered in an appropriate fashion to avoid withdrawal effects and discontinued at least five half-lives plus one additional week for stabilization before Baseline to avoid the possibility of any interaction.

The site physician will consult the prescribing physician to initiate medication tapering for participants, as they must refrain from taking psychiatric medications throughout the study, with some exceptions, see [Section 6.8.2 Permitted Concomitant Medications](#). The prescribing physician's opinion about medication discontinuation should be documented in the participant's study record. Tapering will follow a time course appropriate for the medication based on its half-life, with Baseline scheduled to occur after complete washout (five half-lives plus at least 1 week for stabilization). If the health of the participant worsens after tapering, the participant will be withdrawn from the study and will be treated according to standard clinical practice. This will be recorded in the eCRF.

The therapy team will request information about any changes in medication at each contact. The site physician will be responsible for reviewing and confirming all medications collected during the study.

All medications, non-prescription and prescription, will be collected from Screening through 7 days after the last Experimental Session. From 7 days after the last Experimental Session through Study Termination, only prescription or non-prescription medications taken to treat AEs will be collected. Throughout the protocol, all medications used to treat AEs will be collected, and all changes including discontinuations or additions to medications will be collected. The study team will inquire and document all information about withdrawal and tapering of medications, concomitant medication, and medication adherence in the eCRF Concomitant Medications.

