7.2 Participant Discontinuation/Withdrawal from the Study

- A participant may withdraw from the study at any time at their own request or may be withdrawn at any time at the discretion of the investigator for safety, behavioral, or compliance reasons. This is expected to be uncommon.
- At the time of discontinuing from the study, if possible, an early discontinuation visit should be conducted..
- The participant will be permanently discontinued from the study intervention and the study at that time. The site team will provide the participant with a plan moving forward as described in [Section 8.4.4 Plan Moving Forward](#).
- If a participant develops any Exclusion Criteria that, in the opinion of the Medical Monitor or Site, affects the safety of the participant, the participant will discontinue treatment in Experimental Sessions but may remain in the study for any individual associated non-drug Therapy and Integrative Sessions.
- If a participant withdraws consent for disclosure of future information, the sponsor may retain and continue to use any data collected before such a withdrawal of consent.

- If a participant withdraws from the study, they may request destruction of any samples taken and not tested, and the investigator must document this in the site study records.
- If a participant withdraws, cohort will continue with reduced size.

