8.2 Preparatory Period

Medication tapering will be initiated following enrollment, in collaboration with the prescribing physician, as applicable. Participants will undergo four Preparatory Sessions lasting approximately 90 minutes with the therapy team prior to the first Experimental Session. Adherence criteria for Preparatory Sessions should be followed per the Treatment Manual. The Preparatory Period will last 3-4 weeks, depending on duration of medication tapering. There must be at least 48 hours between Preparatory Sessions. The minimum time to complete the Preparatory Period is 3 weeks. In these visits, the therapy team will work with the participant to prepare for MDMA-assisted therapy, begin building therapeutic alliance, and promote a safe set and setting for confronting trauma-related memories, emotions, and thoughts.

Table 5: Preparatory Sessions

Visit	Individual or Group	Visit Timing
Preparatory Session 1	Group	~1 week (3 to 14 days) after Enrollment
Preparatory Session 2	Group	~1 week (3 to 14 days) after Preparatory Session 1
Preparatory Session 3	Individual	After Preparatory Session 1, but before (Baseline); Preparatory Session 2 and Preparatory Session 3 order may differ; post Taper
Baseline CAPS-5 (T1)	Individual	After Preparatory Session 3, but before Preparatory Session 4
Preparatory Session 4	Group	~3 weeks (17 to 28 days) after Preparatory Session 1; 1 to 14 days before Experimental Session 1

8.2.1 Group Preparatory Sessions 1, 2, and 5

Group Preparatory Sessions during the Preparatory Period will focus on psychoeducation about PTSD, building safety for the therapeutic relationship, developing the therapeutic alliance, and preparing participants for the first Experimental Session. Telephone calls may be scheduled between visits if indicated for tapering, safety, or any further questions about medical history.

At each 90-minute Preparatory Session, the therapy team or other qualified site staff will:

- Inquire about any possible changes in health to ensure the participant continues to meet all eligibility requirements. Record AEs as described in [Section 8.7: Adverse Events, Serious Adverse Events, and Other Safety Reporting](#).
- Inquire about concomitant medication use and adherence.
- Confirm that medication tapering is ongoing or complete, as appropriate.
- If medication tapering is ongoing at Preparatory Session 2, site team to schedule a phone call after tapering and stabilization are complete.

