- Administer Since Last Visit C-SSRS to determine suicidal risk.
- Discuss goals and expectations for the Experimental Session, following standard procedures and techniques described in the Treatment Manual.

At any time during the Preparatory Period, if a potential participant is deemed to be ineligible, the site team will classify them as an Enrollment Confirmation Failure, notify the potential participant that they are unfortunately not eligible for the study, and not schedule additional assessments.

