8.6.1.1 MAPS Adapted Columbia-Suicide Severity Rating Scale (C-SSRS)

The C-SSRS is a clinician-administered measure of suicidal behavior devised to detect potential suicidal thoughts or behaviors during a clinical trial [154]. It consists of a Baseline/Screening

version and a Since Last Visit version that assess suicidal ideation, ideation intensity, and behavior. The C-SSRS consists of a series of questions and can be administered during a face-to-face interview or over the telephone. The Baseline/Screening version will only be administered at the initial Screening visit. All subsequent administrations will utilize the Since Last Visit version. Participants who are discontinuing medications to participate in the study will complete the C-SSRS before and after medication washout. The C-SSRS Intensity scale obtained a Cronbach's alpha of 0.94 for the Since Last Visit form, and Last Visit C-SSRS severity scores were positively correlated with the BDI "suicide thoughts" item [155]. The MAPS Adapted C-SSRS was developed utilizing [name] Columbia Suicide Severity Scale. The MAPS Adapted C-SSRS maintains the content and flow of the standard C-SSRS. The scale was adapted to modify formatting and add additional administrative guidance to reduce rater and data entry errors. The MAPS Adapted C-SSRS has been approved by [name] for use in MAPS Research and is referred to throughout the protocol as C-SSRS. The MAPS Adapted C-SSRS takes approximately 10 minutes to complete.

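### The pre-dosing stop rule ends assessments with no exception for participants already tapering psychiatric medication for the study

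*Protocol*

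**What the plan says.** **The stop rule.** Section 5.4.1 covers enrolled participants who turn out to be ineligible before the first MDMA dose. The site is to "notify the potential participant that they are not eligible for the study, and do not schedule additional assessments. Do not perform the next visit". The participant then receives a plan for moving forward. Section 8.2.1 covers the same period under a different label (Enrollment Confirmation Failure) and tells the site to "notify the potential participant that they are unfortunately not eligible for the study, and not schedule additional assessments".

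**The taper.** Sections 6.8.1 and 8.2 require PTSD-related psychiatric medication to be tapered after enrollment, "with Baseline scheduled to occur after complete washout (five half-lives plus at least 1 week for stabilization"). Section 6.8.1 adds: "If the health of the participant worsens after tapering, the participant will be withdrawn from the study". That person then receives standard care and the event is recorded in the eCRF.

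**Provisions that point the other way.** Section 7.2 says: "At the time of discontinuing from the study, if possible, an early discontinuation visit should be conducted". Section 8.6.1.1 says: "Participants who are discontinuing medications to participate in the study will complete the C-SSRS before and after medication washout".

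**The known risk.** Table 1 in 2.3.1 reports that C-SSRS scores have risen during the Preparatory Sessions of earlier sponsor trials. It attributes this to discussing trauma in preparation, to tapering long-standing medication such as SSRIs and benzodiazepines, or to both.

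**The concern.** The taper is done because the study demands it, and it happens in exactly the window that the stop rule governs. A site that follows 5.4.1 to the letter would end scheduled assessment of someone partly or newly off medication, in the period that the protocol itself flags for suicidality. Ideation that first appears after the stop would then come to light only if the participant, or a clinician outside the study, reported it.

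A site also has to choose between instructions. One section says to schedule nothing more, another asks for an exit visit, and a third expects a second C-SSRS once washout is over. Sites may resolve this differently.

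**Working it through.** No arithmetic applies. The check sets the sections side by side.

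1. **Does the taper fall inside the stop-rule window?** Yes. It begins after enrollment (8.2). The 5.4.1 window runs from enrollment to first dose.

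2. **Does the stop rule exempt tapering participants?** No. Neither 5.4.1 nor 8.2.1 links the stop to taper status, and neither refers to 7.2 or 8.6.1.1.

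3. **Where would the C-SSRS after the taper normally take place?** At Preparatory Session 3, whose Table 5 timing reads "Preparatory Session 2 and Preparatory Session 3 order may differ; post Taper". Section 8.2.2 lists that session's procedures, including the C-SSRS, for eligible participants. Someone stopped earlier does not reach it.

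4. **Does 7.2 fill the gap?** Only in part. The visit is conditional on being possible and is placed at the moment of leaving. For someone stopped in mid-taper it cannot show what happens afterwards.

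5. **Do the other safeguards guarantee a later check?**

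| Provision | What it gives | Why it does not guarantee a later suicidality check |
|---|---|---|
| 6.8.1 | Withdrawal to standard care if health worsens after tapering | Acts on worsening already noticed; schedules nothing to detect it |
| 8.4.4 | Plan at last contact, referral on request | A hand-over, not an assessment |
| 8.7.6.4 | Follow-up of SAEs and AESIs to resolution | Starts from an event already reported |
| 8.2.1 | "Telephone calls may be scheduled between visits if indicated for tapering, safety, or any further questions about medical history", and a call after the taper for those still tapering at Preparatory Session 2 | Part of the preparatory schedule that the stop ends; no C-SSRS specified for the calls |
| 8.7.4 | AE collection from enrollment to the study termination visit | No duty to seek events once participation has ended |

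Each provision helps. Read together, they still leave no stated contact with a C-SSRS after the stop.

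**The case against.** **The sections can be read together.** Not scheduling further assessments may simply mean leaving the protocol visit sequence, with the 7.2 exit visit still held. This reading is reasonable, so a flat contradiction should not be claimed. The tension remains, because 5.4.1 does not say so and a site could as easily read it the other way.

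**The second C-SSRS may no longer apply.** Once a participant is ineligible, there is no study reason to complete washout, and the prescriber may restart treatment. This stands. A reader might use the washout formula in 6.8.1 to count the days left unchecked. The documents do not support that, because they give no half-lives and the endpoint of the interval may never occur. The fix therefore has to allow for restarted medication.

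**Care is handed over, not abandoned.** The prescriber is involved in the taper, the C-SSRS is given at Preparatory Sessions up to the stop, a rise in ideation calls for a risk assessment (8.6.1), and teams must act on serious risk (Table 1). All of this is correct. A reader who inferred that the protocol offers no safety follow-up at all would be wrong. What is missing is narrower: an assured check after the stop.

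**The Schedule of Activities is not in the text at hand**, so the content of the exit visit cannot be seen. This limits the point to the wording of the sections.

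**A reader might also infer that taper-period events in undosed participants will go unanalysed**, because 9.3.5 describes severity summaries for treatment-emergent events while the synopsis objective runs from enrollment. The documents do not support that as a fault. Section 9 calls itself a summary and leaves detail and additional analyses to the SAP. Section 9.3.5 does not confine severity tables to treatment-emergent events, and it plans a summary of suicidality by visit.

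**Conclusion.** The point holds as a patient-safety gap in the wording of 5.4.1 and 8.2.1. The stop rule has no exception for a study-required taper, pulls against 7.2 and 8.6.1.1, and leaves no guaranteed suicidality check after the stop in a period with a reported rise in C-SSRS scores.

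Its size in participants is unknown. Up to 18 are planned, and the protocol states neither how many will taper nor how many will be stopped before dosing, so few people are likely to be affected. The conclusion assumes that the Schedule of Activities adds no post-stop contact. It does not depend on taper being the proven cause of the earlier rise, since Table 1 gives it only as one possible cause. The effect on the efficacy analysis is not at issue. An amendment is warranted because the exposure is imposed by the study and the remedy is cheap.

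**What to change.** In 5.4.1 and 8.2.1, state that the stop ends the protocol visit sequence, and add a cross-reference to 7.2. Then state that a participant who has begun tapering is still offered:

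- the early discontinuation visit in 7.2; and
- one follow-up safety contact, by visit or telephone, with a Since Last Visit C-SSRS and an adverse event review, held after washout or once medication has been resumed.

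Collect adverse events up to that contact. Using one label for this group in both sections would remove a further source of doubt.

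The cost is a wording amendment and one extra visit or call for a small number of participants. The participant remains free to decline.
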